SAE: Serious Adverse Events: generally, any event which causes death, permanent damage,

birth defects, is life-threatening or requires hospitalization is considered an SAE.

SAETRS: Serious Adverse Event Tracking and Reporting System

TLFB: Time line Followback: is a method that can be used as a clinical and research tool to obtain

a variety of quantitative estimates of marijuana, cigarette, and other drug use by asking

clients to retrospectively estimate their usage prior to the interview date.

TNE: Total nicotine equivalents: a urinary measure of nicotine and its metabolite concentrations.

VLNC: Very low nicotine content: cigarettes with much lower levels of nicotine than normal

cigarettes (possibly below addictive levels).

WISDM: Wisconsin Inventory of Smoking Dependence Motives (Brief): a measure of tobacco

dependence.

Study Synopsis

Study Design: Randomized, double-blind (cigarette nicotine content), multi-center study that

will examine the impact of cigarette nicotine content, e-liquid (vaping device)

nicotine content and e-liquid flavor choices on smoking behavior.

Primary Aim: To evaluate the impact of very low nicotine content (VLNC) cigarettes, e-liquid

nicotine content, and e-liquid flavoring on the total number of cigarettes (combined study plus non-study). The hypothesis is that relative to normal nicotine content (NNC) cigarettes, VLNC cigarettes will reduce cigarettes smoked as well as reduce cigarette dependence, reduce exposure to toxicants, increase use of the vaping device and increase abstinence from cigarettes. These differences between VLNC and NNC cigarettes will be greater when participants are provided e-liquids with higher nicotine

concentration and a choice of both tobacco and non-tobacco flavors.

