
3.7. Stratification

Throughout the study, we will stratify by menthol status (no required sample size) and age range (no required sample size 18-24/25+). We recognize that it will likely be more challenging to recruit young adults. We will make use of targeted recruitment strategies (e.g., social media for the recruitment of young adults).

4. Baseline Visit

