Our primary objective is to test the main effects of cigarette nicotine content, e-liquid nicotine content and e-liquid flavors, as well as the interactions among these factors. The primary endpoint will be total CPD (i.e. study plus non-study CPD) based on IVR-Revised. The primary analysis will compare CPD by factor at the week 12 visit using linear regression. Treatment groups should be balanced at baseline, and as a result our primary analysis will only adjust for baseline CPD, week and the three stratification factors (site, age, and menthol preference). This will be considered the "unadjusted model" for the purposes of this document. We will start with a model that includes all two-way interactions between the three factors (note: the three way interaction will not be considered). Two-way interactions that are not significant will be removed from the model and the final model will include the three factors, any two-way interactions significant at the 0.05 levels, baseline CPD, and the three stratification factors. The estimation and testing of main effects in the presence of significant interactions will be completed within levels of the other factor, otherwise, global estimates of the main effects will be obtained. Whenever possible, secondary endpoints will be analyzed following the approach to testing the main effects and interactions described above. Biomarkers of toxicant exposure are expected to be skewed and will be analyzed on the log scale. Likewise, exploratory endpoints will be analyzed following the approach outlined above using a linear mixed model or logistic regression, as appropriate, depending on the type of endpoint (continuous, binary). Finally, we will complete subgroup analyses following the approach described above within each subgroup (age: 18 - 24 vs. 25+; menthol preference; sex). We will not use formal multiple comparison adjustments for secondary endpoints because we have included only 2 outcomes that are likely correlated with each other and the primary endpoint. Likewise, we will not correct for multiple comparisons for our subgroup analyses as they are considered exploratory.

Study staff will make every effort to minimize missing data in the proposed clinical trial. The success of our previous and ongoing trials suggests that missing data will be minimal. Nevertheless, we plan to complete a sensitivity analysis to evaluate the impact of missing data on trial conclusions.

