31.1.3. Data Collection Time Points Identification Numbers

92= Screening Visit

91=Baseline Visit 1

00=Randomization

01= Week 1 visit

02= Week 2 visit

03=Week 3 visit

04= Week 4 visit

06= Week 6 visit

08= Week 8 visit

10= Week 10 visit

12= Week 12 End of Intervention visit

^c Power calculations for our pre-planned subgroup analyses are based on the assumption of 50% of participants in each subgroup defined by age, sex, and menthol status. We are not forcing balance for any of these factors and we therefore acknowledge that the actual power will be larger for subgroups with more than 50% of the sample and lower for subgroups with less than 50% of the sample. ¹ The hypothesized differences for CPD, FTND and log(CEMA) are based on the differences observed between the immediate reduction and control groups at 12 weeks in [name] et al. (submitted)

30= 30-day follow-up visit Additional visit (AV1, AV2, etc) 86 = Termination Visit Identifiers: NCT03185546 Date: 12/31/2019

Project 2: The Impact of Cigarette Nicotine Content, E-cigarette Nicotine Content, and E-cigarette Flavoring on Smoking Behavior

32. Summary of Measures

Duran dama Tabla	Platform/Source	SCRN	BL	RAN	Week	Follow-							
Procedures Table	Platform/Source	92	91	00	01	02	03	04	06	08	10	12	Up 30
Anatabine (spot urine)	UMN Biomarker Core		Х	х	х	Х	Х	Х	Х	Х	Х	Х	х
Mercapturic Acids (1st void urine)	UMN Biomarker Core		х	х				Х		Х		Х	х
Total Nicotine Equivalents (1st void urine)	UMN Biomarker Core		Х	Х				Х		Х		Х	х
Nicotine Metabolite Ratio (saliva)	UMN Biomarker Core		х										
Carbon Monoxide	Paper and REDCap	Х	Χ	Χ	Х	Х	Χ	Х	Х	Χ	Χ	Χ	Х
Urinary Cotinine Test	Paper and REDCap	Х											
BrAC	Paper and REDCap	Χ	Χ	Χ	Χ	Χ	Χ	Χ	Χ	Χ	Χ	Χ	Х
Toxicology Screen	Paper and REDCap	X										Χ	
OTHER ASSESSMENTS													
Identifying Information Form	Paper and Access	Х											
Brief Medical History Questionnaire	Paper and REDCap	Х											
Brief Medical History Follow- Up Questionnaire (if needed)	Paper and REDCap	Х											
Prime MD	Paper and REDCap	Х											
MINI Suicide Subscale	Paper (Source Only)	Х											
Tobacco Use History and Exposure	Paper and REDCap	Х											
Demographics Questionnaire	REDCap	Х											
Smoking Cessation Therapy Use	Paper and REDCap	Х											

CENIC II Project 2													
Procedure Table	Platform/Source	SCRN 92	BL 91	RAN 00	Week 01	Week 02	Week 03	Week 04	Week 06	Week 08	Week 10	Week 12	Follow- Up 30

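### Subgroup analyses repeat the 0.05 interaction selection separately in each subgroup and plan no between-subgroup estimate (minor, exploratory)

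*Combined protocol and SAP*

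**What the plan says.** All of this is in section 29 (Statistical Approach) unless noted.

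- The primary analysis starts from a model with all three two-way interactions among cigarette nicotine, e-liquid nicotine and flavor. Then: "Two-way interactions that are not significant will be removed from the model". The threshold is 0.05.
- What is reported depends on what survives: "The estimation and testing of main effects in the presence of significant interactions will be completed within levels of the other factor". Otherwise a global main effect is given.
- The subgroup plan inherits this: "we will complete subgroup analyses following the approach described above within each subgroup". The subgroups are "age: 18 - 24 vs. 25+; menthol preference; sex".
- Their status is stated openly: "we will not correct for multiple comparisons for our subgroup analyses as they are considered exploratory".
- Section 30 (Power Analysis) gives subgroup power for a main effect and for an interaction, both within a subgroup. Footnote c to its table says: "Power calculations for our pre-planned subgroup analyses are based on the assumption of 50% of participants in each subgroup". It adds that balance is not enforced and that actual power will vary with subgroup size.

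Age and menthol otherwise enter only as adjustment covariates, and sex is not in the model. No section plans a subgroup-by-factor term, a heterogeneity test or a between-subgroup contrast.

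**The concern.** Readers look at paired subgroup results to see whether an effect differs between the two groups. The planned output does not estimate that difference. It gives two separately selected models, and their form can differ by chance: one subgroup may report a factor within levels of another factor while its partner reports the same factor globally.

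A term present in one model and absent from the other is easily read as effect modification, although it only says that one p-value fell below 0.05 and the other did not. This bears on the trial's own hypothesis, which is an interaction. The synopsis says: "These differences between VLNC and NNC cigarettes will be greater when participants are provided e-liquids with higher nicotine". It expects the same for a wider flavor choice.

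What is at stake is how exploratory subgroup results are read, not the trial's main conclusions.

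**Working it through.** **Inputs.** From section 30: CPD effect 6.3, SD 7.2; 480 enrolled with 75% retention, so 360 completers; type I error 0.05 (two-sided assumed); interaction as large as the cigarette effect (6.3, case A) or, for flavor, half of it (3.15, case B). From footnote c: 50% per subgroup, so 180 completers each.

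**Step 1. Reproduce the plan's figure.** With ±1/2 coding, a two-way interaction in a subgroup of n has SE = 4 × SD / √n = 4 × 7.2 / √180 = 2.147.
- 6.3 / 2.147 = 2.93. The noncentral t distribution gives power 0.831. The plan states 0.83.
- 3.15 / 2.147 = 1.47. Power is 0.309.

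Under the selection rule these powers are also the probabilities that a subgroup keeps the term.

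**Step 2. Identical interaction in both subgroups.** The subgroups are disjoint, so the keep decisions are treated as independent. With keep probability p, both keep it with probability p² and exactly one with 2p(1 − p).

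| True interaction, both subgroups | Both keep | Exactly one keeps | Neither |
|---|---|---|---|
| 6.3 | 0.831² = 0.69 | 2 × 0.831 × 0.169 = 0.28 | 0.169² = 0.03 |
| 3.15 | 0.309² = 0.095 | 2 × 0.309 × 0.691 = 0.43 | 0.691² = 0.48 |

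A 20,000-run simulation of the starting model with 180 per subgroup gave 0.278 and 0.422 for exactly one.

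**Step 3. Interaction that truly differs.** The documents do not hypothesize such a difference; these cases are illustrative. The final models give a difference in the interaction only if both subgroups keep the term.
- 6.3 vs 0: 0.831 × 0.05 = 0.04.
- 6.3 vs 3.15: 0.831 × 0.309 = 0.26. In simulation, the mean difference among those trials was 1.38 against a true 3.15, because keeping only significant terms selects large estimates.

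**Step 4. Averaged factor effects.** In a simulation of the whole design (60 per cell, random 75% retention, random 50% split, identical effects in both subgroups), averaged effects from the selected models deviated from full-model effects by an SD of 0.08 to 0.10 CPD. A test of their between-subgroup difference rejected in 4% to 6% of trials, about nominal. Selection therefore barely affects averaged effects; what is missing is their reported difference.

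**Step 5. What one pooled model would deliver.** The between-subgroup difference in an averaged factor effect has SE = 2 × SD × √(1/n₁ + 1/n₂).
- At 180/180: 14.4 × √(2/180) = 1.518. With t on 346 df (1.967), the 95% half-width is 2.99 CPD.
- For a difference in a two-way interaction the SE doubles to 3.04 and the half-width is 5.97. Power is 0.54 for a difference of 6.3 and 0.18 for 3.15.
- At 72/288 (20/80, an assumption; the plan gives no expected share): half-widths 3.73 and 7.46; power 0.38 and 0.13. An uneven split is plausible for age, since section 3.7 says "it will likely be more challenging to recruit young adults".

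**The case against.** The best case for leaving the plan alone has five parts.

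1. **The estimates exist.** The rule cannot be applied without first fitting all two-way interactions in each subgroup. This stands. A reader might infer that a difference in interactions becomes inestimable once a term is dropped. The documents do not support that: it is absent from the final models only, and the gap is a missing commitment to report and compare.
2. **The cause lies elsewhere.** The keep/drop mismatch is inherited from the primary-analysis selection rule. This largely stands. If that rule were replaced and the replacement inherited, only the unplanned between-subgroup difference would remain.
3. **The plan does not ask the question.** No hypothesis says effects differ by age, menthol or sex; the subgroup power columns are within-subgroup; and nothing says a term kept in one subgroup only will be read as heterogeneity. This stands as a limit on severity. A reader might infer that the sponsor will draw false subgroup conclusions, but the rates in step 2 measure mismatched reporting, not wrong conclusions.
4. **The analyses are labeled exploratory.** This also limits severity. The label explains the absence of multiplicity control; it does not supply an estimate of the difference.
5. **The remedy is imprecise.** A half-width of about 6 CPD for a difference in interactions nearly equals the full 6.3 effect. This stands, and it is why those contrasts should not be the main remedy. It does not count against the subgroup-by-factor differences, where an interval shows how little is known and a keep/drop pattern hides it.

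**Conclusion.** The point holds as a minor one. Section 29 reruns the selection in each subgroup and no section plans a between-subgroup comparison, so the planned final models report no estimate of whether a factor effect differs by age, menthol or sex. When an interaction is the same in both subgroups, exactly one keeps it in about 28% of trials (6.3 CPD) or 43% (3.15 CPD), which can pass for a difference where none exists.

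These figures rest on the plan's CPD effect and SD, 360 completers, a 50/50 split and two-sided 0.05. Averaged factor effects are nearly untouched by the selection, and no primary or secondary conclusion depends on this. Severity is minor, and the change is optional.

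**What to change.** **Change.** For each subgroup variable, fit one model on all participants containing the planned covariates, the subgroup main effect (sex has to be added), the three factors, their two-way interactions and the subgroup-by-factor terms, with no data-driven removal. Report the averaged factor effects in each subgroup and their between-subgroup differences with 95% CIs, labeled exploratory and unadjusted for multiplicity.

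**Optional.** Differences in two-way interactions between subgroups may be added from a model that also includes those terms. Give them as estimates with CIs only, and state that non-significance is not evidence of homogeneity.

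**Cost.** SAP wording and three extra models per endpoint, on data already collected. The downsides are low precision, worse if a subgroup is small, and more unadjusted contrasts: three factor differences for each of three subgroup variables is 9 per endpoint, or 18 if the three two-way differences are added for each. They should be read as estimates, not as a set of tests.

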- 7. If a participant fails to attend his/her Randomization Visit within the 21-day allowable visit window, he/she will not be eligible to reschedule this visit or continue participation in the study.
- 8. If there is reason to believe the participant is sharing the study product with other people.

If a participant chooses to withdraw from the study at any time, we will them to return to the lab to return study product and equipment and to receive their final study payment. We will also ask participants who have been randomized if they would like to complete the end of study questionnaires.

27. Investigational Tobacco Product

The Co-Directors of this Center grant, Drs. [name] and [name], have submitted an Investigational Tobacco Product (ITP) application to the FDA to cover the experimental cigarettes being used in this study.

28. Study Endpoints / Outcomes

28.1. Primary Endpoints:

• Total number of cigarettes smoked per day (i.e. study plus non-study cigarettes) as measured by daily Interactive Voice Response (IVR) phone calls. The total number of cigarettes smoked per day will be averaged using the last 7 days prior to the Week 12 visit. We note that subjects have the opportunity to correct data entry errors in MR from calls made since the last visit at each visit (for example, if a subject entered 100 cigarettes instead of 10 cigarettes). In these cases, the original IVR data will be replaced with the corrected data to create a final, cleaned version that will be used for analysis (herein called "IVR-Revised"). A secondary, repeated measures analysis will also be completed using the mean of the total number of cigarettes smoked per day at each visit, calculated using IVR calls from the previous 7 days. In the event that two visits were less than 7 days apart, then the average will be calculated using only days since the last visit.

28.2. Secondary Outcomes:

- Cigarette smoke exposure: mercapturic acid CEMA
- Smoke-free days: the number of days not smoking any combustible products based on IVR-Revised

28.3. Exploratory Outcomes:

- Cigarette characteristics: CES subscale score for Satisfaction
- Discomfort/dysfunction: MNWS total
- Vaping device use: number of days using assigned vaping device (IVR)
- Study cigarettes per day (CPD): the mean cigarettes smoked per day based on 7 days' Daily Interactive Voice Response (IVR)-Revised data before the week 12 visit.
- Cigarette dependence: Total scores on the FTND

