We will compare subjects with and without missing data in order to identify baseline covariates associated with missing data. Our primary approach to handling missing data will be multiple imputation where missing values are imputed using regression models developed from baseline covariates (Little and Rubin, 2002). Daily IVR data will be averaged within a week using complete observations (i.e. we will average the number of cigarettes smoked per day for complete calls). In our previous work ([name] et al., 2015), 90% of weeks had 0 or 1 missed call, while 4% of weeks were completely missing, which suggests that an alternate approach to handling sporadically missed calls will only impact a small number of weeks for the entire trial. Missing

weekly average IVR data (i.e. when all calls in a week are missing) will be analyzed using multiple imputation.

In addition, we will conduct a sensitivity analysis of the primary and secondary endpoints using baseline-carried-forward and last-observation carried forward. The results of these analyses will be compared to the primary analysis to evaluate the robustness of our conclusions.

For the qualitative data, we will use grounded theory to develop hypotheses related to the topics of interest. Interviews will be audio-recorded and transcribed verbatim. The interviews will be analyzed using open and axial coding. Themes will emerge during data analysis, which will be ongoing throughout the project.

30. Power Analysis

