We will enroll 480 subjects (n=60/group) and assume 75% retention at week 12 (i.e. 360 completers) based on our current and previous trials. Power calculations are presented for testing the main effects and the interactions between cigarette nicotine content and e-cigarette nicotine concentration or flavor. Effect size estimates were based on our previous studies of VLNC cigarettes and the assumption that the main effect of e-liquid nicotine content and the interaction between e-liquid nicotine content and cigarette nicotine content will be similar to the effect of cigarette nicotine content. This assumption is supported by the results of [name] and Jones, who found that the effect of transdermal nicotine on use of VLNC cigarettes was as large as the main effect for cigarette nicotine content ([name] & Jones, 2009). The impact of flavors is largely unknown, therefore, we assumed an effect size similar to e-liquid nicotine content (A in table below) as well as one half as large (B in table below). All power calculations were completed assuming a type-I error rate of 0.05. Power calculations for the main effect were completed in PASS 13. Power for testing interactions was calculated by simulation and is consistent with the well-known theoretical relationship between the power for testing main effects and the power for testing interactions.

	Effect size		Pow	Power - Subgroups ^c								
	shown as	Main	Main			Main						
Outcome	Diff (SD)	Effect ^A	Effect ^B	Interaction ^A	Interaction ^B	Effect ^A	Interaction ^A					
			Primar	y Outcome								
CPD ¹	6.3 (7.2)	0.99	0.99	0.99	0.54	0.99	0.83					
Secondary Outcomes												
FTND ¹	1.31 (1.77)	0.97	0.94	0.94	0.41	0.94	0.69					

Log(CEMA) 1	0.51	0.96	0.73	0.73	0.25	0.74	0.44
	(0.92)						

^A Effect size for flavor equal to effect size for nicotine. ^B Effect size for flavor equal to half the effect size for nicotine.

31. Subject Identifier

The subject identifier is an alpha-numeric combination. Example: M-G001 would be Wake Forest University's first subject.

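### The primary multiple imputation is specified from baseline covariates only; followed as written, it shrinks every week-12 effect by about the missing fraction (4% to 25%)

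*Combined protocol and SAP*

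**What the plan says.** Section 29 (Statistical Approach) first compares participants with and without missing data to find baseline covariates related to missingness. It then names as primary approach "multiple imputation where missing values are imputed using regression models developed from baseline covariates". For the primary endpoint, missing "weekly average IVR data (i.e. when all calls in a week are missing) will be analyzed using multiple imputation"; weeks with some completed calls are averaged over those calls.

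The analysis model in the same section is richer: "We will start with a model that includes all two-way interactions between the three factors". A selection rule follows: "Two-way interactions that are not significant will be removed from the model".

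Two figures bear on how much would be imputed. Section 29 reports that in an earlier trial "90% of weeks had 0 or 1 missed call, while 4% of weeks were completely missing". Section 30 plans for 75% retention at week 12, that is, 360 completers out of 480.

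Robustness is to be judged by a "sensitivity analysis of the primary and secondary endpoints using baseline-carried-forward and last-observation carried forward".

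On-study smoking is available as a predictor. Section 28.1 defines a repeated-measures analysis of the "mean of the total number of cigarettes smoked per day at each visit, calculated using IVR calls from the previous 7 days".

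**The concern.** An imputation model should contain at least the terms that the analysis model tests. Here it is narrower. If imputed week-12 values are drawn from a regression on baseline covariates alone, they have the same distribution in all eight cells given those covariates. Mixing them with observed values pulls every main effect and interaction toward zero.

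Adding factor main effects alone is not enough: the main effects recover, but the two-way interactions still shrink. That matters because interactions belong to the primary objective and non-significant ones are dropped. A real interaction that has been shrunk is more likely to be deleted, and the main effect would then be reported globally instead of within levels of the other factor.

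Omitting weekly CPD is a lesser matter. Once factors and interactions are in the model, it costs precision and leaves a smaller bias if dropout depends on smoking during the study.

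**Working it through.** **Inputs.** Section 30: 480 randomized, 60 per cell, 75% retained (360; 180 per factor level), CPD difference 6.3, SD 7.2, type I error 0.05, and a half-size scenario of 6.3/2 = 3.15. Two-sided testing is assumed. Missing fraction *m*: 4% (Section 29, earlier trial) to 25% (Section 30).

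**The plan's own power.**
- Main effect: SE = 7.2 × √(2/180) = 0.759. For 6.3, 6.3/0.759 = 8.30, power 1.00 (stated 0.99). For 3.15, 3.15/0.759 = 4.15, power 0.986 (stated 0.99).
- Interaction, as a difference in differences: SE = 4 × 7.2/√360 = 1.518. For 3.15, 3.15/1.518 = 2.075, power Φ(2.075 − 1.960) = 0.546 (stated 0.54). For 6.3, power 0.986 (stated 0.99).

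The CPD row reproduces.

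**Shrinkage.** A fraction 1 − *m* of each arm carries the effect δ and a fraction *m* carries none, so the expected estimate is (1 − *m*) × δ. If two arms retain r₁ and r₂, the factor is their harmonic mean, 2r₁r₂/(r₁ + r₂). With 30% and 20% missing it is 2 × 0.70 × 0.80/1.50 = 0.747, almost the same as 0.75. This holds when missingness does not depend on outcome.

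**Simulation.** 8 × 60 participants, true effects −6.3 (cigarette) and −3.15 (cigarette by flavor), 20 imputations, Rubin's rules, missing completely at random. The analysis model has the three factors, all two-way interactions and baseline CPD. The documents give no baseline to week-12 correlation, so it was varied from 0 to 0.7.

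| *m* | 6.3(1 − *m*) | 3.15(1 − *m*) | Coverage of 95% CI, cigarette effect | Power for 3.15 interaction, baseline-only | Same, factors and interactions included |
|---|---|---|---|---|---|
| 4% | 6.05 | 3.02 | 93–95% | 0.60–0.87 | 0.64–0.90 |
| 10% | 5.67 | 2.84 | 81–89% | 0.51–0.79 | 0.61–0.87 |
| 25% | 4.73 | 2.36 | 17–47% | 0.28–0.52 | 0.54–0.82 |

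The simulated means agree with the formula. At correlation 0.5, baseline-only imputation gives −6.06 and −3.03 at 4% missing, and −4.70 and −2.33 at 25%. Only correlation 0 is like-for-like with the plan's 0.54: at 25% missing, power is 0.54 with factors and interactions and 0.28 with baseline covariates only. A separate simulation with different correlation assumptions gave 4.75 and 2.32 at 25% missing, with interaction power 0.27 against 0.52.

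**What each addition recovers (25% missing, correlation 0.5).**
- Factor main effects only: −6.27 and −2.32.
- Factors plus two-way interactions: −6.27 and −3.10, interaction power 0.64.
- Also week-4 CPD (assumed weekly correlation 0.8): −6.29 and −3.10, interaction power 0.72.

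**The planned sensitivity analyses (25% missing).** Baseline-carried-forward gives −4.73 and −2.35, the same shrinkage. Last-observation-carried-forward, with the week-4 value and the effect already present by then, gives −6.30 and −3.12.

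**Weekly CPD under outcome-dependent dropout.** Assume 25% missing and dropout odds multiplied by 1.5, 2 or 3 per SD of week-4 CPD. Imputation with assignment but no weekly CPD gives −6.18, −6.05 and −5.80 (bias 2%, 4% and 8%; coverage 95%, 94% and 89%). Adding week-4 CPD gives −6.29, −6.32 and −6.29.

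**Secondary endpoint.** For log(CEMA), 0.75 × 0.51 = 0.38.

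**The case against.** The text is silent on assignment rather than excluding it. The phrase about baseline covariates can be read as naming auxiliaries, with assignment taken for granted, and Section 29 commits all analyses to randomized groups. If factors and interactions are in fact included, the shrinkage disappears. This stands as a condition on the finding. The intent-to-treat commitment does not specify an imputation model, however, and a programmer following the sentence as written would omit the interactions.

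The 25% is visit retention, not the share of CPD weeks with no data. Phone reports may continue after a missed visit, timeline follow-back covers missed calls (Section 9), a missed Visit 12 is rescheduled even outside its window (Section 6.3), and early-termination visits repeat the call review (Section 8.2). So 25% is best treated as an upper bound for CPD, and at 4% the damage is slight. But 4% is a share of all weeks in another trial, and none of these routes recovers participants who are truly lost. CEMA needs a urine sample at the visit (Section 6.4), so phone data cannot fill that gap.

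The power loss is concentrated where the plan was already weak. For a full-size interaction of 6.3, power at 25% missing under the literal reading is still about 0.93, against 0.99 with the correct terms. Last-observation-carried-forward would also show a visible discrepancy if the effect appears early. Both points are fair. Neither removes the bias in the primary estimate, and agreement with baseline-carried-forward would reassure falsely.

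**Conclusion.** The concern holds. As written, the primary imputation model omits terms that the analysis model tests, and week-12 effects shrink toward the null by about the missing fraction. The planned CPD effect of 6.3 would be estimated as 6.05 to 4.73 over 4% to 25% missing. Power to detect it stays at 1.00, but at 10% missing its 95% interval already covers only 81–89% of the time. The largest loss of power is for the half-size interaction: 0.54 to 0.28 at 25% missing on the plan's own assumptions.

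These sizes rest on the literal reading and on missingness unrelated to outcome; coverage and the power ranges also rest on assumed correlations. The true missing fraction for CPD is not settled and may lie well below 25%. The weekly-CPD part is smaller (2–8% bias under assumed dropout odds) and is mainly a matter of efficiency. The point should be fixed before analysis; confidence is medium because the sponsor may already intend to include assignment.

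**What to change.** State in Section 29 that the imputation model for week-12 CPD contains the three randomized factors, all their two-way interactions, baseline CPD, site, age group, menthol preference and the observed on-study weekly CPD averages, with baseline predictors of missingness as auxiliaries. Specify the same structure for the secondary endpoints: log(CEMA), with its week-4 and week-8 values as predictors, and smoke-free days. Note also that baseline-carried-forward shrinks effects by construction, so its agreement with the primary result is not evidence of robustness.

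The cost is SAP wording and slightly more programming. No new data and no additional participants are needed.
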